4.3.3 Visit 3 (Day 2)

- Collect data on operative procedures
- Urine output (should be recorded continuously from time of ICU admission to Day 7, if still in ICU and Foley catheter in place, using 6 hour intervals and by calendar day)
- Collection of AEs/ SAEs
- Collect data on additional amputations
- Collect data on acute renal replacement therapy
- Collect data on plasma or platelet transfusion
- Concomitant medications
- Vital signs (to be taken during the morning tests)
- Critical care parameters (dates and times of assisted ventilation, vasopressor use, ICU /hospital stay)
- Systemic response: mSOFA score (measurements will be collected and scores will be calculated retrospectively).
 - All efforts should be made to obtain the actual measurements of SOFA parameters at these visits-may use SpO2 value if arterial blood gas is not clinically indicated
 - Obtain serum creatinine
 - Obtain CBC with differential and platelet count (sample can be same as that required to be taken in conjunction with the RNA expression profile test sample but must be on the same calendar day as study Day 2)
- Assess lesion status (healing/progression/significant change in appearance) if accessible for visible assessment at time of debridement or routine dressing change
- Collect urine and blood for plasma for storage (AKI biomarker analysis) at 24±4 hours after study drug administration
- Collect whole blood for leukocyte transcriptome (RNA expression) profiling at 24±4 hours after study drug administration
 - CBC with differential required to be obtained in conjunction with sample for RNA expression profile best
- Record Survival

4.3.4 Visit 4 (Day 3)

- Collect data on operative procedures
- Obtain tissue for microbiology if debridement performed on Day 3
- Collect data on acute renal replacement therapy
- Collect data on plasma or platelet transfusion
- Urine output (should be recorded continuously from time of ICU admission to Day 7, if still in ICU and Foley catheter in place, using 6 hour intervals and by calendar

day). Collection of AEs/ SAEs including secondary infections (based on CDC definitions for healthcare associated infections)

- Collect data on additional amputations
- Concomitant medications
- Vital signs (to be taken during the morning tests)
- Symptom-driven interim PE
- Evaluation of adequacy of antimicrobial treatment, based on results from susceptibility testing once the data is available
- Critical care parameters (dates and times of assisted ventilation, vasopressor use, ICU /hospital stay)
- Systemic response: mSOFA score (measurements will be collected and scores will be calculated retrospectively)
 - All efforts should be made to obtain the actual measurements of SOFA parameters at these visits-may use SpO2 value (and record FiO2) if arterial blood gas is not clinically indicated
 - Obtain serum creatinine
 - Obtain CBC with differential and platelet count (sample can be same as that required to be taken in conjunction with the RNA expression profile test sample)
- Assess lesion status (healing/progression/significant change in appearance) if accessible for visible assessment at time of debridement or routine dressing change
- Collect whole blood for leukocyte transcriptome (RNA expression) profiling
 - CBC with differential required to be obtained in conjunction with sample for RNA expression profile best
- Record Survival

4.3.5 Visit 5 (Day7 [±1 day])

- Collect data on operative procedures
- Collect data on acute renal replacement therapy
- Collect data on plasma or platelet transfusion
- Urine output (should be recorded continuously from time of ICU admission to Day 7, if still in ICU and Foley catheter in place, using 6 hour intervals and by calendar day)
- Weight (if easily obtained)
- Collection of AEs/ SAEs including secondary infections (based on CDC definitions for healthcare associated infections)
- Collect data on additional amputations
- Concomitant medications
- Vital signs (to be taken during the morning tests)
- **P**E
- Safety laboratory tests (Chemistry, Hematology)

- Sample for CBC with differential and platelet count can be same as that required to be taken in conjunction with the RNA expression profile test sample
- Assess lesion status (healing/progression/significant change in appearance) if accessible for visible assessment at time of debridement or routine dressing change
- Critical care parameters (dates and times of assisted ventilation, vasopressor use, ICU /hospital stay)
- Systemic response: collect data for mSOFA parameters
 - All efforts should be made to obtain the actual measurements of SOFA parameters at these visits-may use SpO2 value (and record FiO2) if arterial blood gas is not clinically indicated.
- Collect urine and blood for plasma for storage (AKI biomarker analysis)
- Collect whole blood for leukocyte transcriptome (RNA expression) profiling
 - CBC with differential required to be obtained in conjunction with sample for RNA expression profile best
- Record Survival

4.3.6 Visit 6 (Day 10 [±1 day]; perform only if patient is still hospitalized):

- Collect data on operative procedures
- Collection of AEs/SAEs, including secondary infections (based on CDC definitions for healthcare associated infections)
- Collect data on additional amputations
- Collect data on acute renal replacement therapy
- Collect data on plasma or platelet transfusion
- Selected concomitant medications (e.g. vasopressors, antimicrobials)
- Symptom-driven interim PE
- Vital signs
- Critical care parameters (dates and times of assisted ventilation, vasopressor use, ICU /hospital stay)
- Systemic response: collect data for mSOFA parameters
 - All efforts should be made to obtain the actual measurements of SOFA parameters at these visits-may use SpO2 value (and record FiO2) if arterial blood gas is not clinically indicated
 - Obtain serum creatinine
 - Obtain CBC and platelet count (differential not required for Day 10)
- Assess lesion status (healing/progression/significant change in appearance) if accessible for visible assessment at time of debridement or routine dressing change
- Record Survival

4.3.7 Visit 7 (Day 14 [±1 day])

- Collect data on operative procedures
- Weight

- Collection of AEs/SAEs, including secondary infections (based on CDC definitions for healthcare associated infections)
- Collect data on additional amputations
- Collect data on acute renal replacement therapy
- Collect data on plasma or platelet transfusion
- Selected concomitant medications (e.g. vasopressors, antimicrobials)
- Safety laboratory tests (Chemistry, Hematology)
- Collect blood for serum for storage (immunogenicity testing)
- **P**E
- Vital signs
- CRP
- Critical care parameters (dates and times of assisted ventilation, vasopressor use, ICU /hospital stay)
- Systemic response: collect data for mSOFA parameters
 - All efforts should be made to obtain the actual measurements of SOFA parameters at these visits-may use SpO2 value (and record FiO2) if arterial blood gas is not clinically indicated.
 - In case a patient is discharged from hospital prior to these days SOFA parameters should be obtained on the same day of discharge.
- Assess lesion status (healing/progression/significant change in appearance) if accessible for visible assessment at time of debridement or routine dressing change
- Record Survival

All efforts should be made to collect these data, but in case parameters cannot be collected, phone follow-up will be performed, and information that could be collected over the phone will apply.

4.3.8 Visit 8 (Day 21 [±1 day])

- Collection of AEs/SAEs, including secondary infections (based on CDC definitions for healthcare associated infections)
- Collect data on additional amputations
- Collect data on acute renal replacement therapy
- Collect data on plasma or platelet transfusion
- Selected concomitant medications (e.g. vasopressors, antimicrobials)
- Critical care parameters (dates and times of assisted ventilation, vasopressor use, ICU /hospital stay)
- Vital Signs
- Systemic response: collect data for mSOFA parameters
 - All efforts should be made to obtain the actual measurements of SOFA parameters at these visits-may use SpO2 value (and record FiO2) if arterial blood gas is not clinically indicated
 - Obtain serum creatinine
 - Obtain CBC and platelet count (differential not required for Day 21)

• Record Survival

4.3.9 Visit 9 (Day 29 [+2 days])

- Weight
- Collection of AEs/SAEs, including secondary infections
- Collect data on additional amputations
- Selected concomitant medications (e.g. vasopressors, antimicrobials)
- Critical care parameters (dates and times of assisted ventilation, vasopressor use, ICU /hospital stay)
- Systemic response: collect data for mSOFA parameters
 - All efforts should be made to obtain the actual measurements of SOFA parameters at these visits-may use SpO2 value (and record FiO2) if arterial blood gas is not clinically indicated
 - Obtain serum creatinine and albumin
 - Obtain CBC with differential and platelet count
- Collect blood for serum for storage (immunogenicity testing)
- Vital signs
- Collect data on acute renal replacement therapy
- Collect data on plasma or platelet transfusion
- Collection of health economic information: will include several parameters, such as (but not limited to): ICU charges, hospital stay (regular floor) charges, direct costs, indirect costs, reimbursement payments
- Record any hospital re-admissions (if previously discharged for original NSTI related hospitalization)
- Record Survival

All efforts should be made to collect these data, but in case parameters cannot be collected, phone follow-up will be performed, and information that could be collected over the phone will apply

4.3.10 Visit 10 (3 months [±5 days])

The 3-month visit is a follow-up visit to assess the long-term health condition of the patients including assessment of renal function in patients with documented persisting AKI at the Day 29 visit and ascertainment of readmission(s) within 30 days of discharge from original NSTI related hospitalization. Creatinine should be obtained at this visit given the requirement to also obtain serum for storage (for immunogenicity testing). The serum for storage (immunogenicity testing) has priority over creatinine in the order of blood draw if the blood drawn is limited.

4.3.11 Follow-up of Patients

Patients who received the study drug are required to complete the procedures outlined for this clinical study. Exceptions would only include the withdrawal of consent, lost to follow-up or death.

If a patient misses a scheduled visit, attempts to complete the patient data will be made via telephone or rescheduling the visit. After waiting one week for the response, a return-receipt, certified letter containing instructions to call for an appointment will be sent. If no response is obtained within one week after sending the return-receipt letter, the patient should then be considered as lost to follow-up. The returned receipt should be filed with the Investigator's copy of the patient's eCRF. A clinical evaluation should be made based on the last contact with the patient.

Serious Adverse Events (SAEs) occurring within 28 days of a patient receiving IMP will be recorded and processed as described in Section 8.4 of the protocol.

4.4 Sub-study mSOFA = 2

Projected number of patients 60. Note: These patients will not will not receive blinded study drug and are only considered to be an observational cohort.

4.4.1 Screening Visit for patients with mSOFA =2

Evaluation starts once a clinical diagnosis of NSTI was entertained and a decision for urgent surgical wound exploration and debridement was made:

- Obtain ICF
- Verification of Inclusion/Exclusion criteria
- Register in IWR
- Demographics, Medical history, Infected lesion history, Concomitant medications, Vital signs, Height, Weight, calculate BMI, PE
- Recording baseline signs and symptoms and AEs/SAEs (AEs of Day 0 are AEs/ SAEs starting after obtaining ICF until study drug administration)
- Pregnancy test if applicable (blood or urine whichever is faster)
- Baseline mSOFA per section 4.3.1. Baseline mSOFA (where 2 organ components score a 1 or one component scores a 2) will include measurements of the score components in the following organ/systems: respiratory, cardiovascular, renal, coagulation and CNS.
- Post-operative mSOFA score measurements to be performed after surgery and within 6 hours of decision for urgent surgical wound exploration and debridement
 - Repeat complete blood count (CBC)
 - Repeat creatinine
 - Arterial blood gases and FiO2 (if applicable) -may use SpO2 value if arterial blood gas is not clinically indicated
- Critical care parameters (dates and times of assisted ventilation, vasopressor use, ICU and hospital admission and discharge)
- Local lesion assessment and evidence of amputation (excision to a joint space)
- Surgery for NSTI and confirmation of diagnosis. Record time of surgery
- Record Survival

4.4.2 Day 7 or Day 10 Visit [±1 day]

• Collect data on operative procedures

- Collection of AEs/SAEs, including secondary infections (based on CDC definitions for healthcare associated infections)
- Collect data on additional amputations
- Collect CBC and creatinine
- Systemic response: collect data for mSOFA parameters
 - All efforts should be made to obtain the actual measurements of SOFA parameters at these visits-may use SpO2 value (and record FiO2) if arterial blood gas is not clinically indicated.
 - In case a patient is discharged from hospital prior to these days SOFA parameters should be obtained on the same day of discharge.
- Record Survival

4.4.3 Day 14 Visit [±1 day]

- Collect data on operative procedures
- Collection of AEs/SAEs, including secondary infections (based on CDC definitions for healthcare associated infections)
- Collect data on additional amputations
- Collect CBC and creatinine
- Systemic response: collect data for mSOFA parameters
 - All efforts should be made to obtain the actual measurements of SOFA parameters at these visits-may use SpO2 value (and record FiO2) if arterial blood gas is not clinically indicated.
 - In case a patient is discharged from hospital prior to these days SOFA parameters should be obtained on the same day of discharge.
- Record Survival

4.4.4 Day 29 Visit [+2 days] (via phone if patient no longer hospitalized)

- Collect data on additional amputations
- Record Survival

5. TREATMENT OF PATIENTS

5.1 Investigational Medicinal Product

This is a blinded randomized clinical study with 2 treatment groups consisting of 0.50 mg/kg AB103 and placebo. Patients will be randomized in a 1:1 ratio. Each patient will be administered a single intravenous infusion of AB103 based on actual body weight to be infused over 10 minutes. Volume of administration will depend on patients' actual weight.

The study drug can be administered during or after surgical exploration and debridement but no later than 6 hours from the time of clinical diagnosis of NSTI and a decision at the study site for urgent surgical wound exploration and debridement.

AB103 will be supplied in glass vials as a lyophilized powder to be reconstituted with sterile water for injection (WFI). Drug will be reconstituted on the day of its administration, in close proximity to infusion time, and several vials will be pooled together to compose the requested dose. Final volume for infusion will be calculated based on the patient's weight plus adequate priming volume of the IV line.

Placebo will be pyrogen-free, preservative-free sterile 0.9% saline, USP calculated based on the patient's weight, plus adequate priming volume of the IV line.

5.1.1 Presentation and Formulation

AB103 is the acetate salt of a 10 amino acid synthetic peptide. AB103 has homology to amino acid residues 8-15 of the T-lymphocyte molecule CD28, and has D-Ala residues abutted to N- and C-termini to render them more protease resistant. The final formulated drug product is a lyophilized powder containing 10.5 mg of peptide AB103 per vial, 300 mg of mannitol, and 36 mg of NaCl, to be reconstituted with 10.5 mL of sterile WFI. The reconstituted AB103 drug product contains 1 mg/mL of the AB103 peptide. The drug product is filled into clear, 20 mL Type I glass vials with a 20 mm neck, and is then lyophilized. Flurotec-coated rubber lyophilization stoppers are used and 20 mm blue aluminum overseals.

Each vial of the drug product to be used in clinical trials is reconstituted with 10.5 mL of WFI to deliver 10 mL of solution, or 10 mg of AB103. Each vial contains 10.5 mg of peptide AB103, 300 mg of mannitol, and 36 mg of NaCl to be reconstituted with 10.5 mL of WFI.

The lyophilized AB103 drug product is stored at -20° C $\pm 5^{\circ}$ C. Prior to use, each vial of drug (10.5 mg) is solubilized in 10.5 mL of water for injection to generate a drug concentration of 1 mg/mL.

The reconstituted drug product is administered directly and is not diluted prior to administration. To prepare the drug quantity needed for infusion, the contents of several vials need to be pooled together by the study pharmacist, under sterile conditions. The number of vials would depend on the patient's weight, in order to achieve a dose of 0.5 mg/kg. The AB103 drug product will be administered via a syringe infusion pump (may be manually pushed if approved by the medical monitor) in a separate catheter as a single intravenous infusion given over 10 minutes at a dose of 0.5 mg/kg.

The manufacturer of the clinical batches of the drug substance is Bachem Americas, Inc., Torrance CA. The manufacturer of the drug product is Pyramid Laboratories Inc., Costa Mesa, CA.

5.1.2 Storage

IMP will be stored in a limited access area, under appropriate environmental conditions. AB103 should be stored at $-20^{\circ}C \pm 5^{\circ}C$ in a secure, temperature-monitored freezer located in Investigational Drug Service. Reconstituted investigational agents may be stored at room temperature for up to 6 hours Study drug infusion should be performed as soon as possible but within the 6 hour window previously described. If reconstituted drug is not administered it should be discarded.

5.1.3 Administration

AB103 and placebo, formulation and/or preparation of each AB103 or placebo will be performed by the clinical site pharmacist. This process will be performed so that the clinical staff and Investigators will be blinded to each patient's treatment assignment and only the pharmacist will be unblinded. Administration will be by IV infusion using a syringe pump (may be manually pushed if approved by the medical monitor) over a 10 minute period.

5.1.4 Accountability and Destruction of Surplus Investigational Product

Authorization of the site to receive supplies of IMP will be given by Atox Bio/designee upon receipt of relevant essential documentation (for details refer to the study procedures manual). A designated individual at each site will maintain a log of IMP dispensed for each patient. In addition, the Investigator or designated individual at each site will maintain an IMP Accountability Log. This will include the description and quantity of IMP received at the study site, as well as a record of when and to whom it was dispensed.

All used and unused supplies will be retained at the investigational site until the study monitor gives instructions for their return or disposal. The IMP supplied for this study is investigational and under no circumstances may be used for purposes other than those described in this protocol.

The Investigator agrees not to supply the IMP to any person other than the patients participating in the study. IMP may not be relabeled or reassigned for use by other patients except under special circumstances previously approved by Atox Bio.

The Investigator will retain and store all original vials until these vials are inventoried by the unblinded study site monitor. Unless otherwise instructed by the Atox Bio medical monitor, the Investigator agrees to return all original vials at the end of the study, whether empty or containing IMP, to Atox Bio or designee. The Investigator agrees neither to dispense the IMP from, nor store it at any site other than the study sites agreed upon.

A separate unblinded study monitor will ensure proper disposition of original vials whether empty or full with returned or unused IMP. Appropriate IMP disposition documentation will be maintained as part of the source documentation. Permission may be granted for local disposal with supporting documentation.

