1.3 Study Treatment

This is a blinded randomized clinical study in which each patient will receive a single treatment of either 0.50 mg/kg AB103 or placebo (0.9% Sodium Chloride sterile solution) administered intravenously at one of 2 time points: (A) during surgery or (B) shortly after surgery, as long as the administration will be at the earliest time possible and within 6 hours from the clinical diagnosis. Administration will be based on clinical diagnosis of bacterial NSTI at the study site and a decision for urgent surgical wound debridement, and upon confirming the diagnosis of NSTI during the debridement.

The intravenous infusion will be delivered by a syringe pump (may be manually pushed if approved by the medical monitor) over 10 minutes in a separate catheter than that used to deliver other medications. The syringe will identify the contents as "study drug" for protocol ATB-202. All study personnel and clinical staff, as well as the patient, shall remain blinded as to the actual composition of the study drug administered to a given patient. Only the assigned study pharmacist or authorized qualified designate preparing the drug shall be unblinded to the treatment.

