6.2.6.1 Debridement

A debridement is defined as a surgical intervention, performed in the operating room to eliminate a substantial amount of necrotic tissue, based on the description by the surgeon in the operative note. Irrigation of the wound or dressing change in the operating room without tissue removal will not be considered a debridement. Also, minimal procedures to trim margins are not considered a true debridement, nor are bedside procedures, such as a dressing change or Vacuum Assisted Closure (VAC) change.

All operative procedure reports (following appropriate de-identification) will be collected up through Day 14 and any operative reports related to amputations will be collected through Day 28. An adjudication panel of 3 surgeons (investigators involved in the clinical trial) will evaluate the operative reports, in a blinded manner, to assign whether an operative procedure meets the debridement definition as noted above.

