10.4 Data Collection

The Investigators (and appropriately authorized staff) will be given access to an online web-based EDC system which is compliant with 21 CFR Part 11. This system is specifically designed for the collection of the clinical data in electronic format. Access and right to the EDC system will be carefully controlled and configured according to each individual's role throughout the study. In general, only the Investigator and authorized staff will be able to enter data and make corrections in the eCRF/EDC system.

The EDC system/eCRF should be completed for each patient included in the study and should reflect the latest observations on the patients participating in the study. Therefore, the EDC system/eCRFs are to be completed as soon as possible (within 5 working days) after the patient's visit or assessment. The Investigator must verify that all data entries in the EDC system/eCRFs are accurate and correct. If some assessments cannot be done, or if certain information is unavailable, not applicable or unknown, the Investigator should indicate this in the EDC system/eCRFs.

Computerized data-check programs and manual checks will identify any clinical data discrepancies for resolution. Corresponding queries will be loaded into the system and the site will be informed about new issues to be resolved online. All discrepancies will be solved online directly by the Investigator or by authorized staff. Off-line edit checks will be done to examine relationships over time and across panels to facilitate quality data.

After completion, the Investigator will be required to electronically sign off the clinical data.

Data about all study drug dispensed to the patient will be tracked on the EDC system/eCRFs.

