10.5 Access to Source Data

During the study, a monitor will make site visits to review protocol compliance, compare EDC system/eCRFs entries and individual patient's medical records, assess drug accountability, and ensure that the study is being conducted according to pertinent regulatory requirements. EDC system/eCRFs entries will be verified with source documentation. The review of medical records will be performed in a manner to ensure that patient confidentiality is maintained and the study blind is respected.

Checking of the EDC system/eCRFs entries for completeness and clarity, and crosschecking with source documents, will be required to monitor the progress of the study. Moreover, Regulatory Authorities of certain countries, IRBs, IECs, and/or the Sponsor's Clinical Quality Assurance Group may wish to carry out such source data checks and/or on-site audit inspections. Direct access to source data will be required for these inspections and audits; they will be carried out giving due consideration to data protection and medical confidentiality. The Investigator assures Criterium and the Sponsor of the necessary support at all times.

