2.8 Control of blinding and DMC

2.8.1 Randomization and Unblinded Study Statistician

There are three statisticians in this study with different roles:

Blinded primary study statistician – primary lead statistician

Unblinded study statistician – performs randomization and provided back-up

Unblinded DMC statistician independent statistician supporting DMC operations

The role of the unblinded study statistician is:

Perform final randomization,

Provide the randomization to the pharmacy vendor,

Provide randomized allocations in electronic form to the unblinded DMC statistician,

Serve as a backup unblinded statistician.

In advance of study initiation, programming for the blocked randomized treatment allocation with randomized block size was developed. The program to perform this randomization was written in SAS with a Proc IML call to R and is provided in Appendix 6.

A preliminary randomization 'test' seed was used to generate a set of preliminary randomization ID numbers. These were exported to site-specific Excel files and also summarized in a single SAS listing report (RTF format). The unblinded study statistician will use this program to determine final (blinded) randomized allocations and will provide these to the contract drug dispenser in an agreed upon format. A variable indicating the blinded treatment allocations will not be part of the clinical study data to be managed by the data management CRO. This is to eliminate any risk of unblinding through inadvertent data transfer. Therefore, only blinded study data will be available to the blinded primary study statistician and blinded analysis staff.

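### Protocol 5.1.4 gives the blinded Investigator custody of the AB103 vials and lets the Investigator keep the dispensing record; with no placebo vials described, either can reveal the arm

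*Protocol*

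**What the plan says.** **Blinding.** Protocol 1.3 states: "All study personnel and clinical staff, as well as the patient, shall remain blinded as to the actual composition of the study drug". It exempts only the assigned pharmacist or a qualified designate who prepares the drug. Section 5.1.3 repeats the rule: "Investigators will be blinded to each patient's treatment assignment and only the pharmacist will be unblinded". Section 4.2.1 restricts the allocation software to the study pharmacist.

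**Vials.** Section 5.1.4 states: "The Investigator will retain and store all original vials until these vials are inventoried by the unblinded study site monitor". Unless the sponsor's medical monitor instructs otherwise, "the Investigator agrees to return all original vials at the end of the study, whether empty or containing IMP, to Atox Bio or designee". The designee in that last clause is the sponsor's recipient, not a delegate at the site.

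**Logs.** Under 5.1.4 a designated individual keeps a log of product dispensed per patient. The Investigator or a designated individual keeps the accountability log, which covers the description and quantity of product received and the date and recipient of each dispensing. Nothing requires the designated individual to be the unblinded pharmacist.

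**Products.** Sections 5.1 and 5.1.1 describe AB103 as a lyophilised powder in glass vials, several of which are pooled for one dose. Placebo is 0.9% saline. No matching placebo vial, and no kit numbering that would mask the product, is described.

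**The concern.** A site that follows 5.1.4 to the letter hands its blinded Investigator the one set of physical objects that separates the arms. The protocol itself treats the vials as unblinding material, since it has an unblinded monitor count them and a separate unblinded monitor oversee their disposition.

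What is at stake is the surgical part of the endpoints. Both NICCE and the conditional co-primary require no more than three debridements by Day 14 and no amputation after the first debridement. Whether and when to reoperate is a surgeon's judgement, and the operative note is the evidence on which a procedure is classed as a debridement (6.2.6.1). Some investigators are surgeons: "An adjudication panel of 3 surgeons (investigators involved in the clinical trial) will evaluate the operative reports, in a blinded manner". Investigators also judge the relationship of adverse events to study drug (8.2.8). If an Investigator knows the arm while these decisions are being made, a difference between arms could partly reflect that knowledge.

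**Working it through.** **1. Contents of a vial (5.1.1).** 10.5 mg in 10.5 mL gives 10.5 / 10.5 = 1 mg/mL. Delivering 10 mL gives 10 × 1 = 10 mg. This reproduces the protocol's figure.

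**2. Vials per patient.** For AB103 at 0.5 mg/kg, vials = 0.5 × weight / 10, rounded up. The weights are assumed, and priming volume, which the protocol does not quantify, is left out.

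| Weight (kg) | AB103 dose (mg) | AB103 vials, active patient | AB103 vials, placebo patient |
|---|---|---|---|
| 60 | 30 | 3 | 0 |
| 80 | 40 | 4 | 0 |
| 100 | 50 | 5 | 0 |
| 130 | 65 | 6.5, so 7 | 0 |

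At wider assumed weights, 40 kg gives 20 / 10 = 2 vials and 150 kg gives 75 / 10 = 7.5, so 8. The active count never falls to the placebo count of zero, so used vials that can be linked to a patient identify the arm.

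**3. Can vials be linked to patients?** The accountability log makes the link directly for anyone who reads it. Without the log, the link depends on timing. With 290 patients over about 75 sites there are 290 / 75 = 3.9 patients per site on average, so doses at one site will usually be far apart. The documents do not say that vials carry patient identifiers or dates of use.

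**4. Which sentence matters most.** Retention until the monitor's inventory can overlap a patient's 14- or 28-day assessment period, and no inventory interval is stated. Return at study end falls after most outcomes are fixed and matters less.

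**5. The rules side by side.** Sections 1.3, 4.2.1 and 5.1.3 permit one unblinded role at the site: the pharmacist or preparing designate. Section 5.1.4 gives that role's materials to the Investigator, and the custody and return sentences allow no site delegate. Both cannot be followed as written.

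**6. Database and monitoring text.** Section 10.4 says: "Data about all study drug dispensed to the patient will be tracked on the EDC system/eCRFs", and requires the Investigator to verify all entries. It also sets access by role. The only delivery item named is total volume (5.3). Placebo volume is weight-based too (5.1), so volume would not separate the arms if the same mL/kg is used. Section 10.5 has a monitor "assess drug accountability, and ensure that the study is being conducted according to pertinent regulatory requirements" while also comparing eCRF entries with records, and does not say which monitor this is.

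**The case against.** The best case for the plan is that the authors saw the problem and built a firewall. AB103 is kept in a limited-access freezer in the Investigational Drug Service (5.1.2). The pharmacist receives the allocation and prepares the dose. Unblinded monitors inventory the vials and oversee disposition, and the logs may be delegated. Elsewhere 5.1.4 uses the word Investigator for the accountable party, for example in the undertaking about where product is dispensed and stored, so physical handling by the Investigator need not be meant. This stands to the extent that disclosure depends on what a site actually does. It does not remove the conflict: 5.1.2 concerns storage of product, and nothing overrides the custody and return sentences in 5.1.4.

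The endpoints also have protection. The debridement panel reads de-identified reports in a blinded manner against a written definition. Vials at a panel member's own site say nothing about other sites: if the three members come from three average-sized sites, that is 3 × 3.9, or about 12 of 290 patients. Post-screening mSOFA scores are calculated by blinded statisticians (6.2.8), and survival is objective. That protection stands, but the panel can only classify operations that took place and were described. It cannot correct a decision to reoperate or the content of the note.

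A reader might also infer that the eCRF reveals the arm. The documents do not support this. Access is role-based, no vial count or product identity is listed as a field visible to blinded staff, and the allocation variable is kept out of the clinical data. SAP 2.8.1 gives the reason: "This is to eliminate any risk of unblinding through inadvertent data transfer". Likewise, 10.5 requires monitoring to respect the blind and never says that the monitor doing accountability is a blinded one.

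**Conclusion.** The contradiction between 5.1.4 and sections 1.3 and 5.1.3 is real and should be removed. As written, 5.1.4 creates an avoidable route by which a blinded Investigator can learn the arm: about 3 to 7 used vials against none, for assumed weights of 60 to 130 kg. The risk exists where the Investigator personally holds the vials or sees the patient-level log.

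Three stronger readings go too far. It does not follow that every patient's arm is disclosed, because pharmacy storage, delegation and the unblinded monitors may prevent it in practice. It does not follow that the local component is effectively open-label, given the blinded panel. Nor can a size be put on the bias. The observed NICCE difference needed for p≤0.01 is about 0.16 (9.1.2), but any shift in debridement success to set against it would be invented. It would also move NICCE by no more than its own size, because a patient must pass all five components. The stated power and significance levels are not affected.

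**What to change.** Amend Protocol 5.1.4 so that the unblinded pharmacist, or an unblinded designate, retains and returns all vials and keeps both the dispensing log and the accountability log. State that these records, and the vial disposition documents filed with source documentation, are reviewed by the unblinded monitor only. The Investigator can remain accountable for the product without handling it or seeing patient-level records.

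Two supporting clarifications are worth making at the same time:

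- In 10.4, state that any dispensing field that identifies the product is restricted to unblinded roles and is outside the Investigator's verification and sign-off.
- In 10.5, state that drug accountability is done by the unblinded monitor.

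The cost is protocol wording, matching pharmacy instructions and a check of database access rights. The unblinded pharmacist and monitor are already in the plan, so no staff are added, and sample size, endpoints and analysis stay as they are.
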